17.5.3 Analysis of Secondary Endpoints

- 1). Descriptive statistics will be used to calculate the proportion of patients that completed at least 75% of duvelisib doses as documented by the patient pill diaries. The proportion along with an exact 95% confidence interval will be reported.
- 2). Descriptive statistics will be used to calculate the median manufacturing time from the 10 patients that completed at least 75% of duvelisib doses. The median will be reported along with the minimum and maximum manufacturing times.
- 3). A Wilcoxon signed-rank test will evaluate the change in proportion of CD27+/CD28+ and CD4-/CD8- T cells at baseline and at day 15
- 4). Descriptive statistics will be used to calculate the *in vivo* expansion and persistence of CAR-T 19 cells post infusion as measured by serial CAR-T 19 PCR measurements.
- 5). The ORR (complete response or partial response) will be summarized along with an exact 95% confidence interval. Disease response will be based on the RECIST criteria (version 1.1). Please see section 8.2 on the definitions of disease response.

6). The 90 day PFS and OS will be estimated using the Kaplan-Meier method and calculated with corresponding 95% confidence intervals. Please see section 8.3 on the definitions of progressive disease.

7). Descriptive statistics will be used to calculate the frequency of ICU transfers due to CRS and/or neurotoxicity. Descriptive statistics will also be used to calculate the frequency of administration of tocilizumab and/or corticosteroids use for CRS and/or neurotoxicity.

8). Descriptive statistics will be used to assess the frequency of all grade toxicities as defined by CTCAE (version 5.0).

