Protocol Title: Duvelisib Exposure to Enhance Immune Profiles of T Cells in Patients with Diffuse Large B Cell Lymphoma (DEEP T CELLS)

Endpoints:	
Primary Endpoint:
 
• The fold increase in the proportion of T cell phenotypes expressing CD 27/28 (to overall T cell count) after 8 to 15 day exposure to duvelisib 
Secondary Endpoints:
 
• The proportion of duvelisib consumed as evaluated by the patient pill diaries.• Manufacturing time of CAR-T 19 cells in weeks (includes manufacturing failure)• The proportion of CD27/28 double positive T cells and CD4/8 double negative T cells• CAR-T kinetics assessment by PCR• Overall response at 90 days after CAR-T cell infusion defined by the Tumor Response Assessment that are complete responders (CR) and partial responders (PR).• Progression-free Survival (PFS) at 90 days per RECIST 1.1 and Overall Survival at 90 days• ICU transfer due to CRS and/or neurotoxicity or due to the treatment with tocilizumab and/or corticosteroids• Grade III-V toxicities (as defined by CTCAE version 5.0)
Study Population:	20 patients will be enrolled with relapsed/refractory DLBCL or relapsed/refractory follicular lymphoma
Phase:	Pilot
Description of Sites/Facilities Enrolling Participants:	This study will be at Winship Cancer Institute, Emory University.
Description of Study Intervention:	Duvelisib is an oral PI3K inhibitor that is given at a dose of 25mg BID prior to manufacturing of CAR-T cells.
Study Duration:	We estimate that the duration of the study will be approximately 18 months.

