1. To evaluate patient compliance with duvelisib. 2. To evaluate the time required for manufacturing CAR-T using mononuclear cells from duvelisib-treated patients. 3. To describe the frequencies of CD27/28 double positive T cells and CD4/8 double negative T cells 4. To evaluate expansion and persistence of CAR-T cells 5. To evaluate overall response rates following CAR-T cell therapy 6. To evaluate survival rates following CAR-T cell therapy 7. To describe the frequency of CRS and neurotoxicity requiring ICU transfer (for CRS or neurotoxicity) and/or treatment 8. Describe the safety and tolerability profile of duvelisib	1. The proportion of duvelisib consumed as documented by the patient on the pill diaries. 2. Manufacturing time of CAR-T 19 cells in weeks (includes manufacturing failure) 3. The proportion of CD27/28 double positive T cells and CD4/8 double negative T cells 4. CAR-T kinetics assessment by PCR 5. Overall response (per iRECIST) at 90 days after CAR-T cell infusion defined by the Tumor Response Assessment that are complete responders (CR) and partial responders (PR). 6. Progression-free Survival (PFS) at 90 days per RECIST 1.1 and Overall Survival at 90 days 7. ICU transfer due to CRS and/or neurotoxicity or due to the treatment with tocilizumab and/or corticosteroids 8. Grade III-V toxicities (as defined by CTCAE version)

3. Background

Diffuse Large B Cell Lymphoma (DLBCL) and relapsed/refractory follicular lymphoma:

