4.2 Drug/Device Handling

4.2.1 Acquisition and Accountability

Duvelisib will be provided by Secura Bio and will be packaged and labeled by Secura Bio.

Protocol Title: Duvelisib Exposure to Enhance Immune Profiles of T Cells in Patients with Diffuse Large B Cell Lymphoma (DEEP T CELLS)

The sponsor will acknowledge receiving the medication by completing and documenting forms indicating shipment content and condition. Records of duvelisib received at, dispensed from and returned by the study site will be documented in the drug inventory log (DIL). Duvelisib will be dispensed by clinical research staff per the protocol of the Winship Cancer Institute and dispensation of the study drug must be documented. Duvelisib should be taken at approximately the same times on each day and should be taken with 8 oz of water. Patients will be required to maintain a medication diary of each dose of medication. The medication diary (Appendix E) will be returned to clinic staff at the end of completion treatment or at the time of withdrawal from the study.

If a dose of duvelisib is missed by fewer than 6 hours, the missed dose can be taken right away and the next dose taken on schedule. If a dose is missed by more than 6 hours, the dose is skipped the next dose taken at the usual time. Patients will not be allowed to make up missed doses and a missed dose should also be recorded in the patient's diary. Incorrect dosing should also be reported in the patient's diary and documented in the case report form. Damaged medication will be replaced.

Patients will be asked to return all unused duvelisib and packaging at the end of the study or at the time of study treatment discontinuation. Duvelisib supply will be disposed of per Winship's Investigational Drug Service (IDS) SOP. Compliance will be assessed by the investigator and/or study personnel at each patient visit and information provided by the patient and/or caregiver (collection of drug diary) will be captured in the Drug Accountability Form. This information must be captured in the source document at each patient visit. Dose changes and interruptions of study drug must be specifically documented in the patient source documents and eCRF.

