17.5.1 Study Design Endpoints

This is pilot study to examine if exposure to a dual PI3K delta and gamma inhibitor before CAR T cell leukapheresis leads to decreases in manufacturing time and enhanced expression of CD27/CD28+ T cells. Patients who receive at least 75% (23/28 doses) of duvelisib will be evaluable for final analysis. Patients who do not receive 75% of doses will be considered unevaluable and replaced. Patients who do not undergo leukapheresis within two (2) days of completion of the 8 to 15 days of duvelisib will be considered unevaluable and replaced. All patients with any exposure to duvelisib will be evaluable for toxicity (please see section 13.3 on grading of toxicities).

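### The compliance endpoint is the proportion of duvelisib consumed, but the planned analysis never estimates it, and no tablet check or named source supports the dose figure that sets evaluability.

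*Combined protocol and SAP*

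**What the plan says.** The synopsis gives the first secondary endpoint as "The proportion of duvelisib consumed as evaluated by the patient pill diaries". The objectives table in Section 2 agrees: "The proportion of duvelisib consumed as documented by the patient on the pill diaries". Both describe a quantity measured on each patient.

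The only planned analysis, Section 17.5.3 item 1, is descriptive and concerns "the proportion of patients that completed at least 75% of duvelisib doses as documented by the patient pill diaries". It adds: "The proportion along with an exact 95% confidence interval will be reported".

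The same 75% threshold has a second role. Section 17.5.1 states "Patients who receive at least 75% (23/28 doses) of duvelisib will be evaluable for final analysis" and "Patients who do not receive 75% of doses will be considered unevaluable and replaced". Section 17.5.2 limits the primary analysis to patients above 75% of planned doses. Neither section says which record supplies the dose figure.

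On drug accountability, Section 4.2.1 states "Patients will be asked to return all unused duvelisib and packaging at the end of the study" and, in the same sentence, allows return when study treatment is discontinued. It keeps an inventory log, worded at site level, of drug received, dispensed and returned. It has study personnel assess compliance at each visit, with patient or caregiver information (the diary) entered on the Drug Accountability Form. It does not describe counting each patient's returned tablets or comparing them with the diary.

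**The concern.** There are two gaps.

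First, endpoint and analysis are different quantities. A share of patients above a cut-off does not give the amount of drug consumed. A reader of the final report could learn how many patients passed 75% and still not know whether typical consumption was near complete or just above the line. In a pilot that lists compliance as its first secondary objective, that is the information a later trial would need.

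Second, the dose figure also decides who is replaced and who enters the primary analysis, yet its source is not named. The only source named for compliance elsewhere is a self-completed diary. Unused drug comes back to the site, so an independent check is within reach, but the plan does not set one up. With 20 patients, the status of one patient is worth 5 percentage points on any patient-level proportion.

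**Working it through.** **1. The threshold as the plan writes it.** Inputs: 75% and 23/28 (Section 17.5.1); 28 tablets supplied (Section 4.2.2).
- 0.75 × 28 = 21 doses.
- 23/28 = 82.1%.

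The stated figure is therefore not reproduced on 28 doses. On 30 doses, 0.75 × 30 = 22.5, which rounds up to 23.

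**2. The denominator.** Inputs: twice-daily dosing for 8 to 15 days (Section 5.1). If every day carries two doses:
- Planned doses run from 2 × 8 = 16 to 2 × 15 = 30.
- 75% of these is 12 to 22.5 doses (23 as a whole number).
- A fixed 23 exceeds every planned dose for courses of 8 to 11 days (16 to 22 doses).
- A patient who takes all 16 doses of an 8-day course has consumed 16/16 = 100% of that course but 16/28 = 57.1% of 28.

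Until the denominator is defined, neither the percentage consumed nor the 75% share has a single value.

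**3. Whether the planned statistic determines the endpoint.** Assume 18 of 20 patients reach 75%.
- Share reaching 75%: 18/20 = 90.0%, exact (Clopper-Pearson) 95% CI 68.3% to 98.8%.
- Case A: 18 patients at 100%, 2 at 50%. Mean = (18 × 1.00 + 2 × 0.50)/20 = 95.0%.
- Case B: 18 patients at exactly 75%, 2 at 50%. Mean = (18 × 0.75 + 2 × 0.50)/20 = 72.5%.

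The planned output is identical in both cases, while mean consumption differs by 22.5 percentage points. The individual values are illustrative. The conclusion that the share does not fix the mean needs no assumption about diary accuracy.

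**4. How little separates evaluable from unevaluable.** On 28 doses, for a patient who took 20 (20/28 = 71.4%):
- With a cut at 21 doses, one over-recorded dose makes the patient evaluable.
- With a cut at 23 doses, three over-recorded doses do so.

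One patient in 20 is 1/20 = 5 points. The rule in Section 17.5.2 calls the study promising if at least 75% of patients show a two-fold increase, which is 15/20; one fewer gives 14/20 = 70%. The documents give no rate of over-recording, so these figures show sensitivity to a single patient, not an expected error.

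**The case against.** The strongest reply is that this is a descriptive secondary endpoint in a 20-patient pilot with no formal test. The diary is named consistently as its source, and diary data are not unsupervised: Section 4.2.1 has personnel assess compliance at each visit, and dose interruptions go into source documents and the eCRF. That stands, and it keeps the point modest. It does not answer the mismatch between the endpoint and its analysis.

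Four stronger readings are tempting and are not supported.

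- *Tablets are already counted and the count is ignored.* Section 4.2.1 requires return and a site-level log; no per-patient count is stated.
- *Evaluability is set by the diary.* This is a reasonable inference from Sections 4.2.1 and 17.5.3, but Sections 17.5.1 and 17.5.2 name no source. The omission is the finding.
- *Tablets come back months after dosing.* The end-of-study wording permits this, but the same sentence offers treatment discontinuation as an alternative, which may cover normal completion. The timing is ambiguous rather than late.
- *Over-recording dilutes the fold change.* Section 17.5.2 says no in vivo background data exist, and nothing in the documents relates a few doses to the size of the change.

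A reader might also conclude that dispensed minus returned should replace the diary. That measure treats vomited, damaged, lost or unreturned tablets as taken. With 28 tablets supplied and a course as short as 8 days, 28 − 16 = 12 tablets may be left over by design, and each one not handed back would inflate adherence. The count is sound only as a cross-check.

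**Conclusion.** The point holds in this form: the stated compliance endpoint is never estimated, no per-patient tablet count or reconciliation is specified, and the dose figure that sets evaluability has no named source. The first part follows from the text alone; in the illustration, one and the same reported share covers means 22.5 points apart. The second and third parts are gaps in specification. Their effect on results cannot be sized from the documents beyond 5 percentage points per reclassified patient in 20, and nothing shows that any patient would be misclassified. This is a low-cost improvement and not a threat to the primary analysis.

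**What to change.** In Section 17.5.3 item 1, add the per-patient percentage of planned doses consumed, summarised by median and range, beside the share reaching 75% with its exact interval.

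In Sections 17.5.1 and 17.5.2, name the source of the dose figure. Keep the diary as primary. Count returned tablets at the existing Day 15 or apheresis visit and reconcile them with the diary before evaluability is assigned. Report discrepancies and any patient whose evaluability differs between the two sources. Align the return wording in Section 4.2.1 with that visit.

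Separately, reconcile the passages that give 75% as 23/28, the 28 tablets supplied, the 8 to 15 day schedule, and the inclusive (17.5.1) and strict (17.5.2) forms of the threshold, so that the denominator and cut are defined. Which rule applies is for the investigators to settle.

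The added summary costs nothing, since the diary data are already collected. The reconciliation costs a short tablet count at an existing visit. Its limit is that a count is uninformative when tablets are lost, damaged, vomited or only partly returned; such cases should be flagged and left on the diary figure.

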7.1 Apheresis Collection

Patients will need to undergo leukapheresis within two (2) days of completion of the 8 to 15 day treatment of duvelisib. Apheresis will be performed at the Emory Center for Transplantation and Cell Therapy. Peripheral blood mononuclear cells will be collected for CAR-T cell manufacturing according to the standard of care. A single 2-4-hour leukapheresis will be performed on the COBE Optia with the intention of harvesting 3×10^9 white blood cells. If patients are unable to collect the necessary amount required for manufacturing, they can undergo a second leukapheresis. If patients are not able to collect enough product after the second leukapheresis, they will be considered unevaluable and replaced. After apheresis, the quantity of CD27/CD28 double positive T cells, CD4/CD8 double negative gamma delta positive T cells and CD4/CD8 double negative gamma delta negative T cells will be measured via flow cytometry. CAR-T cell manufacturing will be provided by Novartis and are expected to be ready 4 weeks after collection. Failure of the incoming apheresis material or outgoing product to meet the commercial specifications will be discussed with Novartis on a case by case basis.

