- Patients with history of chronic liver disease or veno-occlusive disease
- Patients that are unable to receive prophylactic treatment for pneumocystis, herpes simplex virus (HSV), or herpes zoster (“VZV) at screening
- Patients with history of tuberculosis treatment within the 2 years prior to randomization
- Patients with prior surgery or gastrointestinal dysfunction that may affect drug absorption (e.g., gastric bypass surgery, gastrectomy). Subjects with clinically significant medical condition of malabsorption, inflammatory bowel disease, chronic conditions which manifest with diarrhea, refractory nausea, vomiting or any other condition that will interfere significantly with drug absorption.
- Concurrent administration of medications or foods that are strong inhibitors or inducers of cytochrome P450 3A (CYP3A). No prior use within 2 weeks before the start of study intervention
- Administration of a live or live attenuated vaccine within 6 weeks of randomization

12. Local Number of Participants

We will be recruiting 20 patients at Winship. We are expecting to have to enroll (consent) 30 patients to reach our recruitment goal of 20.. Patients will be registered after signing of the informed consent document and meeting all entry requirements.

13. Recruitment Methods

Investigators, nurses (CRNs), research coordinators (CRCs) and/or data managers review lists of patients who have DLBCL or relapsed/refractory follicular lymphoma and will determine if there are patients who might be eligible for the clinical trial. The CRN/CRC/data manager reviews accessible medical records to screen further for eligibility. The CRN/CRC reviews the eligibility with the physician.

Patients will be identified by their treating physicians. Clinical care team at Winship will inform potential patients about the known benefits and potential risks of a clinical trial as well as other available treatment options.

Protocol Title: Duvelisib Exposure to Enhance Immune Profiles of T Cells in Patients with Diffuse Large B Cell Lymphoma (DEEP T CELLS)

Some of the patients recruited for this protocol will be patients being treated at Emory and under the care of one or more of the study investigators. Some potential patients will be identified by their community treating physician and referred to Emory for possible participation in the clinical trial.

No incentives are provided to patients for trial participation.

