17.5.2 Analysis of Primary Endpoints

All patients that complete >75% of planned duvelisib doses and undergo leukapheresis within 2 weeks of duvelisib treatment completion will be included in the final analysis of the primary endpoint. The primary endpoint of the study to estimate the fold-change increase in CD27/CD28 double positive T cells following *in vivo* exposure to duvelisib from baseline to day 15. Our in vitro studies have shown that culturing DLBCL patients' T cells with 14 days of duvelisib increased the amount of CD27/CD28 double positive T cells from 12.2% to 32.7% (Petersen, et al, supplemental data). However, there are currently no *in vivo* background data to benchmark the expected fold-change CD27/CD28 double positive T cells over a 14-day window. Therefore, with 20 patients, this pilot study will be based on estimation on the fold change increase only and will not include a formal evaluation of the change against a null unpromising fold-change. However, we will consider this study promising if there is at least a two-fold increase in CD27+/CD28+ in at least 75% of patients.

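### The manufacturing-time analysis (17.5.3 item 2) is set at 10 patients where the plan has 20, and does not say how manufacturing failures enter the median, minimum and maximum

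*Combined protocol and SAP*

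**What the plan says.** Section 17.5.3 item 2 gives the analysis of manufacturing time: "Descriptive statistics will be used to calculate the median manufacturing time from the 10 patients that completed at least 75% of duvelisib doses". It continues: "The median will be reported along with the minimum and maximum manufacturing times".

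The trial size is given elsewhere as 20. The synopsis states "20 patients will be enrolled with relapsed/refractory DLBCL or relapsed/refractory follicular lymphoma", and the schema in section 1.2 shows the same total. Section 12 says "We are expecting to have to enroll (consent) 30 patients to reach our recruitment goal of 20". Section 17.5.2 bases the primary analysis on the same number: "Therefore, with 20 patients, this pilot study will be based on estimation on the fold change increase only". Section 17.5.1 makes receipt of at least 75% of doses a condition for the final analysis and replaces patients who fall short.

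The synopsis defines the endpoint as "Manufacturing time of CAR-T 19 cells in weeks (includes manufacturing failure"), and section 2 repeats that definition. On failed material, section 7.1 says only: "Failure of the incoming apheresis material or outgoing product to meet the commercial specifications will be discussed with Novartis on a case by case basis". Section 7.1 also treats patients who cannot yield enough cells after a second leukapheresis as unevaluable and replaces them.

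**The concern.** Two parts of item 2 do not fit the rest of the plan.

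**Count.** Item 2 describes its analysis set by the 75% dose condition. Under 17.5.1 that is a condition every evaluable patient meets, with replacement for those who do not, so the set should be about 20. Attaching the number 10 to it leaves the analyst with a description and a count that cannot both be followed.

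**Failures.** The endpoint definition promises that failures are included. The analysis gives them no time, rank, censoring rule or separate count. The easiest course for an analyst is to summarise the lots that have a completion time. That would favour the hypothesis in section 3.2.1 that manufacture will be faster than in historical controls. It would also hide an outcome that helps motivate the trial: sections 3 and 3.1 cite patients for whom not enough CAR-T cells can be made. Section 17.5.1 names a decrease in manufacturing time as one of the two things the pilot examines, so the summary should be unambiguous.

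**Working it through.** **1. Can 10 be obtained from the plan's own numbers?** There is no sample-size formula, because the study is for estimation only. The candidates are:

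| Route | Result | Equals 10? |
|---|---|---|
| Enrolment target (synopsis, schema, section 12, 17.5.2) | 20 | No |
| Evaluable set after replacement (17.5.1) | 20 | No |
| Consented (section 12) | 30 | No |
| 75% of 20 | 0.75 × 20 = 15 | No |
| 20 reduced by the consent-to-recruitment ratio | 20 × 20/30 = 13.3 | No |

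Ten would be right only if exactly half of 20 enrolled patients reached 75% of doses and none of the others were replaced. That would be a trial result, not a planned number, and 17.5.1 rules it out by replacing such patients. The figure is not reproduced.

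**2. What happens if failures drop out?** With n ordered times, the median sits at rank (n + 1)/2. Dropping k failures from 20 leaves 20 − k times, with the median at rank (21 − k)/2. If failures are kept and ranked last, the median stays at (20 + 1)/2 = 10.5.

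| Failures k | Rank, failures dropped | Rank, failures ranked last |
|---|---|---|
| 0 | 10.5 | 10.5 |
| 1 | 10.0 | 10.5 |
| 2 | 9.5 | 10.5 |
| 3 | 9.0 | 10.5 |
| 4 | 8.5 | 10.5 |

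Each dropped failure moves the reported median half a rank toward faster times. The shift in weeks depends on the spread of times, which the documents do not give.

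**3. Can a median include failures?** Yes. With 20 lots the median is the mean of the 10th and 11th ordered values. If failures are ranked last, the 11th is a real time as long as 20 − k ≥ 11, that is, for up to 9 failures. The maximum has no finite value after a single failure, so the range has to be given among successful lots.

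**4. Is a rule likely to be needed?** The documents give no failure rate, so the rates p below are assumptions. The chance of at least one failure in 20 is 1 − (1 − p)^20.

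| Assumed p | Chance of at least one failure in 20 |
|---|---|
| 2% | 33% |
| 5% | 64% |
| 10% | 88% |
| 20% | 99% |

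Over the same range, the chance of 10 or more failures, which would leave the median without a finite value, is at most 0.3%. Ranking failures last is therefore workable.

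**The case against.** The best defence is that 10 is a wrong number attached to an otherwise clear description. The sentence says which patients are meant, and an analyst would probably use everyone who reached 75% of doses. On failures, item 2 is silent and does not order their exclusion, while the endpoint definition says they count. The endpoint is secondary, has no test or threshold, and plays no part in the criterion for a promising result in 17.5.2. All of this stands. It limits the severity, but does not remove a wrong count from an operative analysis rule or supply the missing rule for failures.

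A reader might also infer four stronger points that the documents do not support:

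- **That a median cannot hold failures.** It can if they are ranked last, as step 3 shows. Only a median of observed times, and the planned maximum, cannot.
- **That slow lots would disappear.** A slow lot that is completed has a time, and the slowest one analysed sets the reported maximum.
- **That the plan permits choosing 10 patients out of 20.** Nothing in item 2 authorises a selection. The conflict is between a count and a description.
- **That precision is lost.** Halving the sample would multiply the large-sample standard error of a median by √(20/10) = 1.41, but the plan reports no standard error or interval for this median.

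**Conclusion.** Wrong as written, and should be fixed. The count of 10 conflicts with four statements of 20 and with the replacement rule, and no route through the documents produces it. Separately, the endpoint includes failures and the analysis does not say how.

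The possible distortion is modest but runs in the favourable direction: half a rank per dropped failure, so rank 9.5 instead of 10.5 with 2 failures in 20. It arises only if the analyst drops failures, which the plan neither requires nor prevents. The figures assume that replacement brings the evaluable set to 20; the chance that a rule is needed rests on an assumed failure rate of 2% to 20%. The primary analysis, the safety analysis and enrolment are unaffected.

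**What to change.** In 17.5.3 item 2, replace "median manufacturing time from the 10 patients that completed at least 75% of duvelisib doses" with wording to this effect:

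*Median manufacturing time among all evaluable patients (planned 20). Lots that fail manufacture are ranked as longer than any observed time when the median is computed. The number and proportion of failures are reported with an exact 95% CI. The minimum and maximum are reported among successful lots and labelled as such.*

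A supportive summary of all products sent for manufacture could be added. Nothing in the documents requires it, and it describes a wider population than the evaluable set.

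The new wording relies on the definition of an evaluable patient, so the statements of that definition need to be reconciled at the same time. Section 17.5.1 equates 75% with 23 of 28 doses, but 23/28 = 82.1% and 75% of 28 is 21. Sections 17.5.1 and 17.5.2 also give different windows for leukapheresis (two days and two weeks).

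The cost is one paragraph of wording, settled before the analysis, with no new data. The reported median may come out slightly less favourable than one computed on successful lots only.
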